5.7 Diet/Activity/Other Considerations

5.7.1 Diet

Subjects should maintain a normal diet unless modifications are required to manage an AE such as diarrhea, nausea, or vomiting.

5.7.2 Contraception

Pembrolizumab may have adverse effects on a fetus in utero. Furthermore, it is not known if MK 3475 has transient adverse effects on the composition of sperm.

For this trial, male subjects will be considered to be of non-reproductive potential if they have azoospermia (whether due to having had a vasectomy or due to an underlying medical condition).

Female subjects will be considered of non-reproductive potential if they meet 1 of the following criteria:

- She is postmenopausal, defined as at least 12 months with no menses without an alternative medical cause. In women <45 years of age who are not using hormonal contraception or hormonal replacement therapy, a high follicle-stimulating hormone (FSH) level in the postmenopausal range may be used to confirm a post-menopausal state. In the absence of 12 months of amenorrhea, a single FSH measurement is insufficient.
- She had a hysterectomy and/or bilateral oophorectomy, bilateral salpingectomy or bilateral tubal ligation/occlusion, at least 6 weeks prior to screening.
- She has a congenital or an acquired condition that prevents childbearing.

Female and male subjects of reproductive potential must agree to avoid becoming pregnant or impregnating a partner, respectively, while receiving trial drug and for 120 days after the last dose of trial drug by complying with 1 of the following:

- Practice abstinence from heterosexual activity.

Abstinence (relative to heterosexual activity) can be used as the sole method of contraception if it is consistently employed as the subject's preferred and usual lifestyle and if considered acceptable by local regulatory agencies and European Research Councils (ERCs)/IRBs. Periodic abstinence (eg, calendar, ovulation, symptothermal, post-ovulation methods, etc.) and withdrawal are not acceptable methods of contraception.

- Use (or have their partner use) acceptable contraception during heterosexual activity.

Acceptable methods of contraception are‡:

- Single method (1 of the following is acceptable):
 - Intrauterine device (IUD)
 - Vasectomy of a female subject's male partner
 - Contraceptive rod implanted into the skin
- Combination method (requires use of 2 of the following):
 - Diaphragm with spermicide (cannot be used in conjunction with cervical cap/spermicide)
 - Cervical cap with spermicide (nulliparous women only)
 - Contraceptive sponge (nulliparous women only)

- Male condom or female condom (cannot be used together)
- Hormonal contraceptive: oral contraceptive pill (estrogen/progestin pill or progestin-only pill), contraceptive skin patch, vaginal contraceptive ring, or subcutaneous contraceptive injection

‡If a contraceptive method listed above is restricted by local regulations/guidelines, then it does not qualify as an acceptable method of contraception for subjects participating at sites in this country/region.

Subjects should be informed that taking the study medication may involve unknown risks to the fetus (unborn baby) if pregnancy were to occur during the study. In order to participate in the study they must adhere to the contraception requirement (described above) for the duration of the study and during the follow-up period defined in Section 7.2.2 - Reporting of Pregnancy and Lactation to the Sponsor. If there is any question that a subject will not reliably comply with the requirements for contraception, that subject should not be entered into the study.

5.7.3 Use in Pregnancy

If a subject inadvertently becomes pregnant while on treatment with pembrolizumab, the subject will immediately discontinued from trial treatment. The site will contact the subject at least monthly and document the subject's status until the pregnancy has been completed or terminated. The outcome of the pregnancy will be reported to the Sponsor without delay and within 24 hours if the outcome is a serious adverse experience (e.g., death, abortion, congenital anomaly, or other disabling or life-threatening complication to the mother or newborn). The study investigator will make every effort to obtain permission to follow the outcome of the pregnancy and report the condition of the fetus or newborn to the Sponsor. If a male subject impregnates his female partner the study personnel at the site must be informed immediately and the pregnancy reported to the Sponsor and followed as described above and in Section 7.2.2.

5.7.4 Use in Nursing Women

It is unknown whether pembrolizumab is excreted in human milk. Since many drugs are excreted in human milk, and because of the potential for serious adverse reactions in the nursing infant, subjects who are breast-feeding are not eligible for enrollment.

5.8 Subject Withdrawal/Discontinuation Criteria

Subjects may withdraw consent at any time for any reason or be dropped from the trial at the discretion of the investigator should any untoward effect occur. In addition, a subject may be withdrawn by the investigator or the Sponsor if enrollment into the trial is inappropriate, the trial plan is violated, or for administrative and/or other safety reasons. Specific details regarding discontinuation or withdrawal procedures; including specific details regarding withdrawal from Future Biomedical Research, are provided in Section 7.1.4 – Other Procedures.

A subject must be discontinued from the trial for any of the following reasons:

- The subject or legal representative (such as a parent or legal guardian) withdraws consent.

5.8.1 Discontinuation of Treatment

A subject must be discontinued from treatment (but may continue to be monitored in the trial) for any of the following reasons:

- The subject or legal representative (such as a parent or legal guardian) withdraws consent for treatment
- Confirmed radiographic disease progression outlined in Section 7.1.2.5.1 (exception if the Sponsor approves treatment continuation).

Note: For unconfirmed radiographic disease progression, please see Section 5.2.2

Note: A subject may be granted an exception to continue on treatment with confirmed radiographic progression if clinically stable or clinically improved, please see Section 7.1.2.5.1

- Unacceptable adverse experiences as described in Section 5.2.1.2 and Section 7.2
- Any progression or recurrence of any malignancy, or any occurrence of another malignancy that requires active treatment
- Intercurrent illness other than another malignancy as noted above that prevents further administration of treatment
- Investigator's decision to withdraw the subject
- A confirmed positive serum pregnancy test
- Noncompliance with trial treatment or procedure requirements
- Recurrent Grade 2 pneumonitis
- The subject is lost to follow-up
- Completed 24 months of treatment with pembrolizumab

Note: 24 months of study medication is calculated from the date of first dose. Subjects who stop pembrolizumab after 24 months may be eligible for up to 1 year of additional study treatment if they progress after stopping study treatment provided they meet the requirements detailed in Section 7.1.5.2.1.

- Discontinuation of treatment may be considered for subjects who have attained a confirmed CR that have been treated for at least at least 24 weeks, receiving at least 2 doses of pembrolizumab beyond the date when the initial CR was declared. Subjects who stop pembrolizumab with SD, PR, or CR, may be eligible for up to 1 year of pembrolizumab if they experience disease progression after stopping pembrolizumab. This retreatment is termed the Second Course Phase (Retreatment) and is described in detail in Section 7.1.5.2.1.
- Administrative reasons

The End of Treatment and Follow-up visit procedures are listed in Section 6.0 (Protocol Flow Chart) and Section 7.1.5 (Visit Requirements). After the end of treatment, each subject will be followed for 30 days for AE monitoring (serious adverse events will be collected for 90 days after the end of treatment as described in Section 7.2.3.1). Subjects who discontinue for reasons other than progressive disease will have post-treatment follow-up for disease status until disease progression, initiating a non-study cancer treatment, withdrawing consent or becoming lost to follow-up. After documented disease progression each subject will be followed by telephone for OS until death, withdrawal of consent, or the end of the study, whichever occurs first.

5.9 Subject Replacement Strategy

Additional subjects may be enrolled in a given cohort to ensure that the required number of evaluable subjects in each cohort is achieved. A subject that discontinues the trial for progressive disease or a drug-related AE will not be replaced and will be counted in the evaluable population of subjects for the respective cohort. Further details are provided in Section 8.1.3.

5.10 Beginning and End of the Trial

The study begins when the first subject signs the informed consent (either pre-screening consent or main study consent). The end of the study may be designated as the time point when all subjects have discontinued the study or are a minimum of 6 months post initial study medication administration. If, by the end of the study, there remains at least 1 subject still on study treatment for at least 6 months, the subject(s) may enter additional treatment cycles. At this point a database lock of the trial may occur to allow the analysis of the study data. Any remaining subjects may continue to receive study medication and be seen by the investigator per usual standard of care for this subject population. In addition, the investigator will be expected to monitor for and report any serious adverse events, events of clinical interest, and pregnancies, as detailed in Section 7.2.3 (Serious Adverse Experiences). The subject is considered on study until such time that he/she meets any of the discontinuation criteria and written notification is given to the Sponsor.

Upon study completion, subjects are discontinued and enrolled in a pembrolizumab extension study.

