Tumor Biopsies/Archival Tissue Collection/Correlative Studies Blood													
Archival or Newly Obtained Tissue Collection ^e	X ^s												
Correlative Studies Blood Collection ^e		X ^t				X ^t				X ^t			

- a. Treatment cycles are 2 weeks. Imaging should be performed every 8 weeks initially (56 days \pm 7 days) and after 6 months, imaging assessments should be performed every 12 weeks regardless of any treatment delays (i.e. Screening visit, Cycle 5, Cycle 9, Cycle 13 and then every 6 cycles (12 weeks)).
- b. In subjects who discontinue study therapy without documented disease progression, every effort should be made to continue monitoring their disease status by radiologic imaging^p every 8 weeks (\pm 7 days) in the first 6 months and every 12 weeks (\pm 7 days) after Month 6 until (1) the start of new anti-cancer treatment, (2) documented disease progression, (3) death, or (4) the end of the study, whichever occurs first.
- c. Pre-screening informed consent must be obtained prior to sending an archival sample to the vendor for characterization. Subjects that do not have archival tissue available must sign the main study consent prior to undergoing a newly obtained biopsy.
- d. Written consent must be obtained prior to performing any protocol specific procedure. Results of a test performed prior to the subject signing consent as part of routine clinical management are acceptable in lieu of a screening test if performed within the specified time frame (e.g., within 28 days prior to the first dose of trial treatment). Baseline number will be assigned when the study informed consent is signed.
- e. Leftover samples may be kept for Future Biomedical Research if the subject signs the Future Biomedical Research (FBR) consent.
- f. Prior medications – Record all medications taken 28 days before the first dose of trial treatment. Concomitant medications – Enter new medications started during the trial and 30 days after last dose of trial treatment regardless of when the Safety Follow-up visit occurs.

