7.1.2.5.3 Tumor Imaging During Trial

Tumor imaging may be performed by CT or magnetic resonance imaging (MRI), but the same imaging technique should be used in a subject throughout the trial. Imaging should be performed every 8 weeks (56 days ± 7 days) from the first dose of trial treatment or more frequently if clinically indicated. After 6 months, imaging should be performed every 12 weeks (84 ± 7 days). Imaging timing should follow calendar days and should not be delayed for delays in cycle starts or withholding of pembrolizumab cycle intervals.

Per RECIST 1.1, PR and CR response should be confirmed by a repeat radiographic assessment not less than 4 weeks from the date the response was first documented. The tumor imaging performed for confirmation of response may be performed at the earliest 4 weeks after the first indication of response, or at the next scheduled scan, whichever is clinically indicated.

Imaging should continue to be performed until documented disease progression, the start of new anti-cancer treatment, withdrawal of consent, death, or the end of the study, whichever occurs first. Disease progression should be confirmed at least 4 weeks after the first scan indicating progressive disease in clinically stable subjects. Subjects who have unconfirmed disease progression may continue on treatment until progression is confirmed provided they have met the conditions detailed in Section 7.1.2.5.1.

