8.2.5.1 Statistical Methods for Efficacy Analyses

Efficacy will be evaluated separately in each cohort. For the primary efficacy endpoint investigator assessed RECIST 1.1 best ORR, the point estimate, repeated confidence interval, and adjusted p-value for testing the RECIST 1.1 response rate is greater than 10% for each disease indication will be provided using a truncated sequential probability ratio test [32], which is a specific instance of an exact binomial group sequential design for a single arm trial with a binary outcome. Subjects in the primary analysis population (FAS) without response data will be counted as non-responder. Interim decisions may be made based on confirmed or unconfirmed response assessments (see Sections 8.2.7 and 8.2.9). However, the final analysis (if enrollment in a given indication expands to 22 subjects) will require a confirmation assessment for all subjects who develop a CR or PR.

For PFS endpoint, Kaplan-Meier (KM) curves and median estimates from the KM curves will be provided as appropriate. Subjects without efficacy evaluation data or without survival data will be censored at Day 1.

Table 14 summarizes the key efficacy analyses.

Table 14 Analysis Strategy for Key Efficacy Variables

Endpoint/Variable (Description, Time Point)	Primary vs. Supportive Approach [†]	Statistical Method	Analysis Population	Missing Data Approach
Primary Hypothesis #1 – Within Indication				
Best ORR using RECIST 1.1 by site radiology assessment (each disease indication evaluated separately)	P	Truncated sequential probability test	FAS	Subjects with missing data are considered non-responders
Best ORR using modified RECIST 1.1 by site radiology assessment (each disease indication evaluated separately)	S	Truncated sequential probability test	FAS	Subjects with missing data are considered non-responders
Secondary Endpoints/Objectives – Within Indication				
PFS using RECIST 1.1 criteria by site assessment	P	Summary statistics using Kaplan-Meier method	FAS	Censored at last assessment
PFS using modified RECIST 1.1 criteria by site assessment	S	Summary statistics using Kaplan-Meier method	FAS	Censored at last assessment
OS	P	Kaplan-Meier method	FAS	Censored at last assessment
DOR by site assessment	P	Summary statistics using Kaplan-Meier method	All responders	Non-responders are excluded in analysis

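### The earliest permitted database lock falls before a response first seen on the week-24 scan can be confirmed, so the last-dosed subjects may lose such responses from the final ORR

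*Combined protocol and SAP*

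**What the plan says.** **End of study and lock.** Section 5.10 allows the end of the study to be designated when all subjects have discontinued or "are a minimum of 6 months post initial study medication administration". It continues: "At this point a database lock of the trial may occur to allow the analysis of the study data". After that, "Any remaining subjects may continue to receive study medication and be seen by the investigator per usual standard of care", and subjects pass to an extension study.

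**Scans.** Section 7.1.2.5.3 states: "Imaging should be performed every 8 weeks (56 days ± 7 days) from the first dose of trial treatment". After 6 months the interval becomes 12 weeks. The Section 6.1 flow chart gives the sequence as "Screening visit, Cycle 5, Cycle 9, Cycle 13 and then every 6 cycles (12 weeks"; with 2-week cycles the on-treatment scans fall at weeks 8, 16 and 24, then week 36.

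**Confirmation.** Section 7.1.2.5.3 says a CR or PR should be "confirmed by a repeat radiographic assessment not less than 4 weeks from the date the response was first documented", either by a scan from 4 weeks onward or at the next scheduled scan.

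**Endpoint.** Section 8.2.3.1 defines best ORR by confirmed CR or PR during the study. Section 8.2.5.1 lets interim decisions use unconfirmed responses, but the final analysis at 22 subjects "will require a confirmation assessment for all subjects who develop a CR or PR". Section 8.2.7 sets success at 6 or more confirmed responders of 22.

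No section sets a later data cut-off for ORR or makes the lock wait for a pending confirmatory scan.

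**The concern.** Sections 5.10, 7.1.2.5.3 and 8.2.5.1 do not fit together for a subject who has only the minimum follow-up. The plan schedules a third scan, would accept a first response on it, and then permits the lock before that response can meet the endpoint's own definition. Imaging under this protocol stops at the end of the study, and no section brings a confirmation obtained in the extension study back into this analysis.

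At stake is a small downward bias in the primary endpoint. It matters somewhat more here than in many trials, for two reasons. Section 4.2.3.1 itself expects responses that come later than with cytotoxic agents. The final success rule is also a sharp count, so a cohort with 5 confirmed responders and one pending fails where 6 would succeed.

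**Working it through.** **1. Calendar**

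- Earliest lock for the last subject: 6 months = 365.25/2 ≈ day 183.
- Week-24 scan: 168 ± 7 = days 161-175.
- Earliest confirmation: 161 + 28 = day 189; 168 + 28 = day 196; 175 + 28 = day 203.
- Confirmation at the next scheduled scan: week 36 = day 252, or 252 + 7 = day 259 at the end of the window.
- Even the best case, day 189, is 189 − 183 = 6 days after the permitted lock.
- A response first seen at week 16 (day 112) can be confirmed from day 140, or on the week-24 scan, so it is safe.

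**2. Who is exposed**

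The Section 5.10 condition covers all subjects in all 20 cohorts. A subject first dosed *d* days before the trial's last subject is at day 183 + *d* when the lock becomes possible. Confirmation is out of reach only if 183 + *d* is less than the confirmation day:

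- confirmation at 4 weeks: *d* below 189 − 183 = 6 to 203 − 183 = 20 days;
- confirmation at the scheduled scan: *d* below at most 259 − 183 = 76 days.

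Illustration (assumption): the 24-month trial duration in Section 1.0, less 6 months, leaves 18 months (about 548 days). With even accrual of 440 subjects, 440 × 20/548 ≈ 16 are dosed in the last 20 days, under 1 per cohort. In the last 76 days it is 440 × 76/548 ≈ 61, about 3 per cohort.

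**3. The plan's own power figure**

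Table 15 gives 80% power at a true ORR of 35%, with 0.14 probability of stopping for futility and an average sample size of 20.1. I used an exact binomial recursion over the bounds of Tables 11 and 12, with looks at every n from 6 to 22.

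| Rule at true ORR 35% | Result |
|---|---|
| Any efficacy crossing counts as go | power 81.4% (stated 80%) |
| Futility stops, otherwise enrol to 22 | P(futility) 0.145, average n 20.1 |
| Futility stops, then ≥6/22 at the end | 77.7% |
| ≥6/22, no monitoring | 83.7% |

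The last two rows are the baselines here, because the question concerns the confirmed count at the final analysis.

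**4. Effect of the lost responses**

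Let *k* of a cohort's 22 subjects be exposed, and let *f* be the share of responders first seen at week 24. The documents give no value for *f*; 10-20% is an assumption. Without monitoring, the count is Binomial(22 − *k*, 0.35) plus Binomial(*k*, 0.35(1 − *f*)). With monitoring, futility looks count unconfirmed responses, as Section 8.2.9 allows, and the final count loses the late ones.

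| Exposed subjects *k* | P(≥6/22), no monitoring, *f* = 10% to 20% | With Table 12 futility stops |
|---|---|---|
| 0 | 83.7% | 77.7% |
| 1 | 83.3% to 83.0% | 77.4% to 77.2% |
| 3 | 82.6% to 81.4% | 76.9% to 76.0% |
| 6 | 81.3% to 78.8% | 76.0% to 74.0% |

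The expected bias in a cohort's ORR is (*k*/22) × 35% × *f*. For *k* = 3 this is 3/22 × 35% × 0.1 ≈ 0.5 points to 3/22 × 35% × 0.2 ≈ 1.0 point.

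**The case against.** The strongest reply is that Section 5.10 grants a permission. Six months is a minimum, the end of study may be designated then, and the lock may follow. A reader might infer that the loss is certain. It is not: it arises only if the sponsor uses the earliest date. This objection stands.

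Second, Section 8.2.5.1 can be read as requiring that the confirmatory scan be in hand before the final analysis, which would close the gap. That reading is possible. But the sentence, like its counterpart in Section 8.2.9, sets no time and does not refer to the lock. It can equally mean that unconfirmed responses do not count. The missing-data rule should not be relied on either way: it covers subjects without response data, and a subject with three scans has such data. The loss follows from the endpoint definition alone.

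Third, a reader might extend the calculation to a cohort with all 22 subjects at minimum follow-up. The trial-wide condition does not support that. It would need a whole cohort to be first dosed in the trial's final weeks.

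Fourth, the bias is downward, so it cannot inflate the type I error. Future study planning may also start on an interim efficacy crossing that counts unconfirmed responses. Both points are right and limit the consequence.

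Finally, any fixed cut-off leaves some later response unconfirmed. That is true of a bare date, and it is why the remedy below is tied to a named assessment.

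**Conclusion.** The calendar conflict is real and follows from the stated schedule without assumptions: at the 6-month minimum, no on-schedule week-24 response can be confirmed before the permitted lock. Its effect depends on the sponsor locking at the earliest date, and it reaches only subjects first dosed within about 6-20 days of the last subject, or up to about 76 days if confirmation waits for week 36.

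The size is small. With 1 to 3 exposed subjects in a cohort and an assumed 10-20% late share, the chance of reaching 6/22 at a true ORR of 35% drops by about 0.4 to 2.3 percentage points without monitoring (83.7 − 83.3 to 83.7 − 81.4), and by 0.3 to 1.7 points with futility stops (77.7 − 77.4 to 77.7 − 76.0). Six exposed subjects, a cohort concentrated at the end of accrual, would cost up to 4.9 points (83.7 − 78.8). The documents support neither a certain loss nor loss across a whole cohort. This is a cheap improvement to a stated rule; it does not undermine the design.

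**What to change.** In Sections 5.10 and 8.2.5.1, state that the data cut-off for the final ORR will not occur until every subject with a CR or PR first documented by the 6-month (week-24) assessment has either had the confirmatory assessment already called for in Section 7.1.2.5.3 or left imaging follow-up. In practice this is about 29-30 weeks after the last first dose (203/7 = 29), or about 37 weeks (259/7) if confirmation is left to the next scheduled scan.

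**Cost.** The lock is trial-wide as written, so a delay would apply to the whole trial: about 3 weeks (20/7) to 11 weeks (76/7), and only when such a confirmation is pending. No extra patients are needed, and no scan beyond those the protocol already calls for.
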